4.1. SUBJECT POPULATION

Approximately 30 subjects total will be enrolled in this study following a 2:1 ratio (intervention: control). The study will be conducted at the University of Rochester Medical Center. Over 250 patients are newly implanted with a defibrillator per year and over 1,000 patients are followed within the system.

- Gender and Age of Subjects: Male and female subjects aged 18 years to 85 years. We expect to enroll about 25% women.
- Racial and Ethnic Origin: There are no restrictions on race or ethnicity in this study. We expect to enroll about 25% minority subjects.

Inclusion Criteria

- 18 to 85 years of age on the date of randomization
- ICD implantation for primary prevention in patients with ischemic and non-ischemic cardiomyopathy ≥ 3 calendar months from date of enrollment
- SMART Phone or tablet with Bluetooth capability with internet access
- No other identifiable reversible cause explaining the left ventricular dysfunction

Exclusion Criteria

- CRT implanted.
- LVEF $> 45\%$ in the last echocardiogram or other clinic imaging performed.
- Medtronic device generator and/or device components not implanted
- Unstable clinical condition, life threatening arrhythmia
- Heart failure hospitalization within the preceding 3 calendar months
- Cognitive impairment
- Severe renal dysfunction (eGFR < 30 ml/min/m²)

- Serious known concomitant disease with a life expectancy of < 12 calendar months
- Non-ambulatory NYHA class IV
- Pregnancy

Inclusion of Vulnerable Populations:

- Vulnerable populations: Women of childbearing potential are included if they are currently on the medications to be optimized (beta-blockers, diuretics and Sacubitril/Valsartan).

4.2. STUDY INTERVENTIONS

Please see section 7 entitled Study Procedures for integrated description that includes the study interventions.

Devices

Implantable Cardioverter Defibrillator: This study is not studying devices but will utilize data already clinically used and available from implantable defibrillators (ICD). Patients qualify for this study once they and their clinical team has decided to have an ICD implanted for primary prevention of sudden death as part of standard of care. All ICDs are FDA approved and will be used per the FDA indications.

Wristband Sensors: The study will also use a commercially available wearable wristband sensor (Garmin) to collect functional data. The Garmin Vivo Smart wristbands will be used to passively collect data. This data will not be used for optimizing the Guideline directed medical management. These wristbands use 3D accelerometers and other sensors to measure basic human function such as movement and heart rate patterns and provides high resolution raw data for research purposes. The URMC investigators have evaluated the actual device and found it ideal for the proposed study. It is wrist-worn, fully waterproof watch like band that has been scientifically validated in both adults and children. They are compact, wrist-worn, rechargeable battery- operated whose physical characteristics are similar to a small wristwatch attached at subject's wrist. The following technical specifications have been provided by the manufacturer.

- The Garmin Vivo Smart utilizes an accelerometer to monitor the occurrence, degree of and duration of motion. The sensor integrates the degree and speed of motion and produces an electrical current that varies in magnitude. An increased degree of speed and motion produces an increase in voltage. The device stores this information as activity counts. The shape of the sensor makes it most sensitive to motion in certain orientations. It also measures heart rate, and other basic physiologic variables as well as time. However, it is sensitive to motion in all directions.
- The Garmin wearable wristband data can also be downloaded and programmed to provide the needed data. Both wristband sensors are similar in form factor attached to the

subject's wrist. It then accumulates subject activity as counts for a specific period of time known as the *epoch length*.

Datos App: The Datos App is commercially available in the app store marketplace and will be free to use by study subjects

1. Activity data collected by the Garmin watch will be transmitted via Bluetooth/Wifi to a smart device (tablet or smartphone with installed app). The app collects subject activity data passively from the Garmin watch.
2. Survey data, including the Weekly e-Survey and KCCQ will be performed using the Datos app platform to make the surveys convenient and user-friendly for subjects. REDCap may also be used as an alternative for the surveys if Datos is unavailable.

The study team will have access to the patients' activity data, however these data are passively collected and not used in clinical decision-making. These data are collected for future data analysis. These data will be coded by study subject number. The Datos app can be used on iOS and Android operating platforms. All data will then be synced to a secured cloud database via Internet connection as indicated in the Electronic Data Security Assessment Form. Study subjects will delete the Datos app when instructed to do so by study staff.

PHYSICAL PROPERTIES OF WRISTBAND WEARABLES

Parameter	Value
Sampling rate	10-100Hz
Battery type	Rechargeable (Garmin)
Battery life	Rechargeable (Garmin)
Accelerometer sensitivity	+8g
Waterproof	Yes to 10 meters
Frame cover	plastic
Wrist band	Nylon or compatible

- The accelerometer wristband and any monitoring equipment that needs to have data downloaded will be done remotely to minimize number of research visits.
- The devices will be assigned to the subject by a study team member. Devices will be stored in a locked office that only the study team has access to. Subjects will be asked to return the devices upon completion of the study. Medical- grade disinfectingwipes will be used to clean the wristband wearable monitors after each subject use.

5. RECRUITMENT METHODS

This study will identify potential subjects for recruitment using the UR CTSI Research Participant Registry, STUDY00001978, and by local referrals to URMC electrophysiology lab or clinic patients or patients who have recently undergone an ICD device implant with cardiomyopathy. Investigators have routine access to medical records that will be screened.

Subjects who meet inclusion will be identified by or referred to the investigator. The initial contact via study team will be by way of the clinical service treating provider obtaining permission for the study team to approach patient. Phone contact will occur if the initial contact has been made by the clinical team first. The study team will introduce and gauge interest about participating in the study. The investigator will notify the research coordinator if the patient is interested to continue the informed consent process.

The research coordinator will discuss the study details with patient either in clinic or via phone depending on patient preference. The consent form may be taken home from clinic or mailed so the patient will have adequate time to think about study and/or discuss with family if applicable. Consent will be obtained in person or via mail consent by coordinator or investigator at the study site.

6. CONSENT PROCESS

The site investigator and/or study coordinator will consent subjects in this study. The consent document will be used as a guide for the verbal explanation of the study and will be the basis for a meaningful exchange between the investigator and the potential subject. The subject's signature provides documentation of agreement to participate in a study but is only one part of the consent process. The consent document will not serve as a substitute for discussion and the potential subject will be invited to ask any questions or concerns that will be answered by the study team members. Once a participant indicates that he or she does not want to take part in the research study, this process stops. The potential subject will be given sufficient opportunity to consider whether or not to participate. Refusal to take part or withdraw from the study at any time will not interfere with the future medical treatment.

The consent will be archived in study binders with consent checklist and kept at study center offices at the enrolling site. The subject will be provided with a copy of the signed original consent form for their records. Subject enrollment log will be maintained throughout study.

7. STUDY PROCEDURES

After consent, subjects will undergo/agree to the following study-related procedures (Consent and Enrollment may be done at separate visits):

- Garmin wearable wristband is provided for daily wear. Subjects should wear the wristband as often as possible. Subjects will return the Garmin wristband at 6 months.
- Quality of life questionnaire: KCCQ and a 3-question weekly electronic survey (e-survey) will be completed via the commercially-available Datos app platform. The survey

asks questions about how you are feeling, have you felt any symptoms, and the quality of your health status. The KCCQ should take 10 minutes to complete and the 3-question weekly e-survey should take 3 minutes to complete. Research staff will follow up with subject if weekly e-survey has not been completed for 2 weeks. REDCap may also be used as an alternative.

- Electronic medical record data regarding clinical history, medications, device implantation, and follow-up data will be collected for 12-month period.
- PROMIS data collected from medical record for 12 months, ICD data, medications, and other office visits/ hospitalizations/ unplanned visits standard of care will be available for chart review.
- Will participate in virtual visits, with phone visits occurring in the event a virtual visit is not possible. For those subjects in the intervention group, medications will be adjusted to optimize to medical guidelines; for those in the control group, no medications will be adjusted, but the subject will have the opportunity to share any changes in their medical status and any questions for the study staff. The control group will only receive their usual care and will not have their medications optimized by the research team. Visit time is approximately 30 minutes.
- Virtual Visit Overview with Subjects: Study staff will provide basic instruction to the subject on the use of Zoom. Study staff will show subject an example of a Zoom virtual visit to help them better understand the Zoom program before the first monthly virtual visit. Subjects will be invited, via e-mail link, to the Zoom meeting from the URMC HIPAA secured Zoom portal. They will then click on the invite link and will be directly connected with the study staff member. The Zoom Help Center (<https://support.zoom.us/hc/en-us>) may also be used as an online resource to help troubleshoot the virtual visit.
- Blood samples may be taken as part of the study if a subject is randomized to the intervention group and the study team adjusts diuretic medications as clinically indicated. These blood samples are for patient safety and are routinely ordered to assess kidney function when a patient is taking diuretics. Labs will be ordered via a paper requisition and billed to the study. Research study staff will follow up within 3 days of result return.
- Future Use Blood Sample (optional)

Method of Assigning Subjects to Treatment

Study enrollment using the electronic data capture system that is available 24/7 to all study personnel. Patients will be randomized in a 2:1 fashion to either intervention or conventional management. Randomization will be conducted using a computer random number generator.

Follow-up Schedule (See also Table 1)

Following enrollment, all subjects will have scheduled follow-up visits (phone, electronic or telemedicine) by the study team at monthly intervals following enrollment and baseline testing.

CIED-derived physiologic and functional reports will be available to the study team only for patients assigned to the GDMT-medical optimization intervention group.

All subjects will be followed for a time-period of 6-months. Medical record data will be collected for a 12-month period.

The following time-points will be assessed:

- *Enrollment (V0):* Baseline clinical characteristics, existing echocardiographic measures and NYHA class will be recorded. Additional tests will include a 6-minute walk test and KCCQ questionnaire. Garmin wristband is provided.
- *Randomization (V1):* subjects will be randomized to an intervention arm of CIED-based medical optimization vs. conventional management.
- *Monthly virtual visits by research team (V1a):*
 - Conventional group: questions about symptoms, changes in activity levels, medications and adverse events. No additional CIED data provided to the subjects' usual clinical care providers since they will follow their own standard routine for CIED-monitoring.
 - Intervention group: virtual visits for medical optimization and prescription changes to medications based on CIED-reports and decision flowchart.
- *3-months (V2):*
 - Intervention group: office visit for clinical assessment, including physical exam and NYHA class. Clinical and adverse events.
 - Control group: office visit for device interrogation, medical record review, report any changes in standard care, NYHA class.
- *6-months (V3):*
 - Intervention group: Physical exam, NYHA class, 6-minute walk test, KCCQ, clinical and adverse events.
 - Control group: office visit for device interrogation, medical record review, report any changes in standard care. NYHA class, perform 6-minute walk test and KCCQ.

The CIED and Garmin wearable wristband physiologic (activity, heart rate, oxygen saturation) and functional data will be continuously captured by the study's core lab for all patients throughout follow-up. The Garmin Wristband sensor data will not be used for intervention. The

lab/data capturing process is HIPAA compliant and Garmin wristband is identified through a study ID number and patient name is not registered into with wristband.

Timeline	Consent/ Enrollment (may be separate visits)	Performed Weekly	1m +- 7d	2m +- 7d	3m +- 7d	4m +- 7d	5m +- 7d	6m - 7d/+14d	Thru Month 12 Chart Review No Visits
Informed Consent	✓								
Randomization	✓								
Medical History	✓								✓
Vital Signs: BP, weight, RR	✓				✓			✓	
Review Inclusion/Exclusion Criteria	✓								
Medication List	✓		✓	✓	✓	✓	✓	✓	✓
Blood Sample Repository: Optional	✓								
Remote CIED data acquisition	✓	Data Acquired remotely throughout study							
Remote Wearable data (Garmin) acquisition	✓	Data Acquired remotely throughout study							
QOL: KCCQ	✓							✓	
Weekly E-Survey	✓	✓							
6MWT	✓							✓	
Virtual Visit	✓		✓	✓		✓	✓		
In-person Clinic Visit: Physical Exam NYHA Class CEID Interrogation	✓				✓			✓	

Medication Optimization – Management Regimen

The clinical research team managing the intervention group will follow standard clinical discretion in adjusting medications as appropriate and will use the medication flowchart (Figure 1) that includes considering the clinical physiologic data that is available in ICD devices and used clinically.

[figure not shown]
The medication adjustment flowchart reminds clinicians to consider any device data such as heart rates and activity etc. as well as patient reported outcomes to optimize medication dosing to meet guideline directed medical therapy which is associated with long term survival benefit.

Dose adjustment will be based upon the monthly reporting of data acquired from the CIEDs focusing on the following medications: Loop diuretics (e.g., furosemide, bumetanide, torsemide) unless the subject is not indicated, is contraindicated, or is intolerant of loop diuretics; and beta-blockers unless the subject is not indicated, contraindicated, or is intolerant of beta-blockers. The choice of selective or non-selective beta-blockers use is left to the clinician Investigator's discretion. Blood work may be ordered to assess kidney function within 1-2 weeks of changes to diuretic medications.

Additional virtual follow up after dose adjustments is not prohibited and left to investigator team discretion as needed.

Figure 1: Medication Flowchart

Medication Decision Module

Medication Optimization Guideline

- If Average HR > 70 bpm + Stable OptiVol + Stable per patient symptoms, Then increase BB per the recommendation (drug dosage table)
- If Average HR < 60 bpm + Stable OptiVol + Stable per patient symptoms, Then no change in BB until next follow up
- If Average HR > 70 bpm + increased volume per OptiVol + reduction in capacity per patient symptoms, then adjust diuretics first and subsequently (in the next virtual visit BB if HF still >70 bpm)
- If Average HR < 70 + increased volume per OptiVol + reduction in capacity per CIED activity and patient symptoms, then, adjust diuretics without BB
- Similar flow process for Activity guided exercise prescription which would look to optimize daily activity/exercise steps upward toward target if OptiVol, HR, patient reported symptoms are consistent that no acute decompensation is occurring or imminent.

Clinical Discretion applies to all medication adjustments

Plans for return of research results:

- A summary of the study research results will be provided to all patients after completion of the study, analysis and publication of a peer-reviewed publication. Raw data and individual will not be available.
- For both groups, if there are life-threatening incidental findings during the study which require clinical intervention, the subject's primary clinical team will be notified in a time frame appropriate for the clinical event, via eRecord, secured email, or in person as applicable. It is understood that the usual care control group will have significantly less monitoring and data will not be analyzed at the same frequency as the intervention group.

8. RISKS TO SUBJECTS

This is an interventional study in subjects who are qualified for a standard-of-care implantation of an ICD device. The study is not evaluating any medical device. The intervention is to include the use of currently available device data to guide medication management and optimize guideline directed medical therapy.

There is some risk of associated with the use of any medication. It is important to note that in this study, we are using standard of care and recommended guideline directed medications already indicated in this population of heart failure patients; which are often associated with reduced mortality and improved outcomes. We are not testing new medications. Medications inherently may be associated with side effects. The clinical research team is experienced in cardiovascular trials and the clinical management of patients with heart disease/heart failure and will be monitoring for any adverse effects and adjust medications accordingly.

The study team may be notified if you receive other health care services at URMC or its Affiliates (e.g., visit to the emergency room). In addition, the following individuals may know you participated in research and may see results of testing conducted for this study:

- Staff at the University of Rochester Medical Center and its Affiliates (e.g., Strong Memorial Hospital, Highland Hospital, URMC primary care, specialist physician offices) who have a reason to access your electronic health record.
- Health care providers who are involved in your care at a facility that is not part of the University of Rochester Medical Center and its Affiliates and who have reason to access your electronic health record.
- Individuals who request a copy of information from your health record for activities such as treatment or payment (e.g., medical insurance companies, worker's compensation).

All study data will be deidentified using a unique study ID number. The study ID number will also be stored in a separate document (study log) that is linked to identifying information about you such as your name.

10. POTENTIAL BENEFITS TO SUBJECTS

There are no direct benefits that the subject can expect to receive as a result of participating in this study. It is possible that there may be a benefit to participating in the intervention group as these subjects will have a comprehensive study team managing their medications and possibly adjusting medications based on reported symptoms.

11. COSTS FOR PARTICIPATION

There are no additional costs to the subject. All medication optimization follows standard of care guidelines. Medication changes are billed to subject's insurance per standard of care.

12. PAYMENT FOR PARTICIPATION

Subjects will be paid up to \$100.00 for taking part in this study. Subjects will receive \$50.00 for each completed in-clinic follow up visit. Subjects will not be paid for visits that they do not complete. Compensation is paid by check and may take 4-6 weeks to process.

If subjects withdraw from the study prior to the 3-month visit, then subjects will not receive any compensation.

Additionally, subjects will be reimbursed for parking fees via a URMC parking voucher at the "in-person" research-related clinic visits.

13. SUBJECT WITHDRAWALS

Subjects will be advised in the written informed consent forms that they have the right to withdraw from the study at any time without prejudice. Subjects may be withdrawn as lost to follow-up by the investigator if their data on ICD interrogation and survival are not available for 7 months from last device interrogation. These subjects will not undergo any additional study activities after withdrawal. If a subject becomes pregnant during the course of a study, they will continue to be monitored but no longer be part of the interventional arm. Data collected will be used up to the date of withdrawal.

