4. STUDY DESIGN

The study is a randomized pilot clinical trial. The Coordination and Data Center (CDC) is at the University of Rochester. Each site will directly interface with the subjects for activities such as consent, testing, study team virtual and in person-visits.

The study will enroll approximately 30 subjects with ischemic and non-ischemic cardiomyopathy previously implanted with an ICD for primary prevention of sudden cardiac death. Subjects are followed for 6 months. Clinical, functional, and digital biomarker data will be captured related to: activity, heart rate, blood pressure, weight, blood biomarker BNP, quality of life status, and clinical events. Electronic health records will be monitored for 12-month period to collect/record study data.

Study data will be entered by site staff using a web-based data entry system at the University of Rochester for data management, analysis, and coordination of logistics.

The study duration is 2.0 years: including an estimated 3-month initiation phase; an estimated 8-month enrollment phase; and an estimated 6-month follow-up phase; with subsequent data analysis.

Primary Endpoint

The primary outcome of this study is the rate of change in medical management with beta-blockers, diuretics and Sacubitril/Valsartan (defined as initiation, termination, switch, or dosing adjustment) in the intervention group compared to usual care at 6 months.

Secondary outcomes

- Recurrent changes to medication type and dosing reflecting ongoing personalized optimization.
- Mean changes in functional status (measured by 6-minute walk distance) in the intervention vs. control groups.
- Percentage change in average daily activity level between the first month following discharge and the last month of the study (6th month) will be compared between intervention and control groups.
- Quality of life (measured by Kansas City Cardiomyopathy Questionnaire) from index discharge to 6 months after discharge in the intervention vs. control groups.
- Healthcare utilization as determined by unplanned office visits and hospitalizations.
- Cardiac hospitalizations and all-cause mortality.
- Laboratory biomarkers.

Screening

Potential subjects will be screened using electronic records to ascertain prior ICD implantation per inclusion/exclusion criteria. The potential subject's health care provider will be contacted for permission to approach the patient for further screening and if eligible, obtain consent.

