Addition or removal of heart failure medications and changes in medication dosage will be left to the discretion of the treating physician. Upon completion of 6 month follow up the subjects will no longer require study visits and will return study equipment. We plan to collect study data from the electronic health record through 12 months at which time no further data will be collected.

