17. DATA ANALYSIS PLAN

Statistical Methods

Primary Statistical Hypothesis

To test the hypothesis that a multidisciplinary team intervention using pre-specified medication

dosing regimens guided by Cardiac Compass-Optivol data will increase the rate of change in beta-blocker and/or diuretic prescription (defined as initiation, termination, or dose adjustment) in the intervention group compared to usual care at 6 months.

Statistical Test Method and Sample Size Considerations

The primary outcome of this study is the rate of change in medical optimization (changes in heart failure medications and dosing) guided by CIED physiologic and patient engagement app data that are used together with pre-specified medication dosing regimens over 6 months. The rate of change in HF medications (beta-blocker, diuretic, and Sacubitril/Valsartan) will be compared between the multidisciplinary team intervention guided by CIED physiologic digital data group and usual care control group using chi-square analysis. We estimate that the rate of medication change will be 10% in the conventional group based on our URMC ICD database, as compared to 60% in the intervention group. Accordingly, a sample of approximately 30 patients will be required to provide a power of 80% and a 2-sided alpha of 0.05, accounting for 10% drop out rate. The comparison of the rate of recurrent medication adjustments between the two study groups will be assessed using negative binomial regression analysis and is expected to result in greater than 80% power (possibly 99%) based on the expected rate of multiple medical changes (at the monthly virtual visits) in the intervention group.

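### Section 13 does not separate stopping study visits from refusing record access, so early withdrawals lose or shorten a 6-month endpoint that planned record review could usually complete

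*Combined protocol and SAP*

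**What the plan says.** Section 13 lets subjects withdraw at any time. It then states: "These subjects will not undergo any additional study activities after withdrawal", and closes with "Data collected will be used up to the date of withdrawal". Two situations are treated separately. A subject may be declared lost to follow-up when interrogation and survival data "are not available for 7 months from last device interrogation". A subject who becomes pregnant is handled thus: "they will continue to be monitored but no longer be part of the interventional arm".

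Section 4 defines the primary endpoint as change in beta-blockers, diuretics or sacubitril/valsartan, "defined as initiation, termination, switch, or dosing adjustment) in the intervention group compared to usual care at 6 months". Section 17 compares the arms by chi-square and sizes the trial "accounting for 10% drop out rate". It gives no analysis set, no missing-data rule and no rule for partial follow-up.

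The plan also describes a data source that needs no visit. Section 7 says: "Electronic medical record data regarding clinical history, medications, device implantation, and follow-up data will be collected for 12-month period". Section 4 says: "We plan to collect study data from the electronic health record through 12 months". The schedule in section 7 (Table 1) includes the medication list in its chart-review column through month 12. Section 4 requires changes made at the intervention arm's virtual visits to be entered in the medical record.

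**The concern.** The trial asks for daily wristband wear, weekly surveys and monthly calls. A patient may want to stop these without objecting to a later look at the chart. Section 13 offers no such option, so the data cut-off that suits a refusal of record access also applies to a patient who has only had enough of the visits.

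The primary outcome is a yes/no result at 6 months. A change recorded before withdrawal still counts. A patient without one has an unknown result, and a chi-square test cannot use part of a follow-up period. Dropping such patients means the arms compared are no longer the arms randomised. Counting them as unchanged compares, say, 1 month of observation with 6. Hospitalizations, unplanned visits and deaths after withdrawal are also lost to the secondary outcomes. With about 10 controls, one patient is worth 10 percentage points of that arm's rate.

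**Working it through.** **Inputs.** From section 17: 10% control and 60% intervention change rates, two-sided alpha 0.05, 80% power, 10% drop-out, about 30 patients. From section 4: 2:1 allocation, so 20 intervention and 10 control.

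**The plan's own figure.** Pooled two-proportion formula with k = 2 and mean rate (0.10 + 2×0.60)/3 = 0.433:

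n(control) = [1.96×√(0.433×0.567×1.5) + 0.842×√(0.10×0.90 + 0.60×0.40/2)]² / 0.50² = (1.190 + 0.386)² / 0.25 ≈ 9.9, so 10 control and 20 intervention, 30 in total.

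Thirty is thus the evaluable number. Allowing for 10% drop-out would give 30/0.9 = 33.3, so 34. That modest shortfall is a separate matter. For this point, 10% of 30 is 3 patients.

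**Assumptions not in the documents.** Withdrawal at month 1; constant hazard of first change; after stopping, intervention patients change at the usual-care rate. Two splits of the 3 withdrawals: 2 intervention + 1 control, and 3 + 0 as an extreme.

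**Probability of a change for a withdrawn patient.**
- Intervention, data cut at month 1: 1 − 0.4^(1/6) = 14.2%
- Control, data cut at month 1: 1 − 0.9^(1/6) = 1.7%
- Intervention, chart followed to month 6: 1 − 0.4^(1/6) × 0.9^(5/6) = 21.4%
- Control, chart followed to month 6: 10%

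**Expected rates.**
- 2+1, truncated: intervention (18×0.60 + 2×0.142)/20 = 55.4%; control (9×0.10 + 1×0.017)/10 = 9.2%; difference 46.2 points
- 2+1, chart followed: intervention (18×0.60 + 2×0.214)/20 = 56.1%; control 10%; difference 46.1 points
- 3+0, truncated: intervention (17×0.60 + 3×0.142)/20 = 53.1%; control 10%; difference 43.1 points
- 3+0, chart followed: intervention (17×0.60 + 3×0.214)/20 = 54.2%; control 10%; difference 44.2 points
- Withdrawn patients dropped: 60% v 10%; difference 50 points. That is 50 − 46.1 = 3.9 points (2+1) or 50 − 44.2 = 5.8 points (3+0) above the comparison of everyone randomised.

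**Power**, by exact enumeration of the 2×2 tables with the uncorrected chi-square at 0.05:

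| Withdrawals | Truncated at month 1 | Dropped | Chart followed to month 6 |
|---|---|---|---|
| 2 + 1 | 75.5% | 78.9% (18:9) | 74.6% |
| 3 + 0 | 68.4% | 83.7% (17:10) | 70.7% |

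With no withdrawals at all, power is 81.5%. For withdrawal at months 2 to 4, chart follow-up moves power by about −0.8 to +1.5 points relative to truncation.

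**Reading of the result.** Continued record review does not recover power. Dropping patients gives the highest figure in each row because it removes those whose treatment stopped, so it no longer estimates the difference between the randomised groups. Truncation happens to give almost the same expected difference in the 2+1 case, and is about 1 point low in the 3+0 case. These are averages under assumptions that do not link withdrawal to the patient's own prospects of a change. Nothing in the plan ensures that.

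**The case against.** **The sentence may be harmless.** The closing sentence of section 13 can be read as the usual assurance that data already collected are kept. Whether passive record review is a study activity is not said, and nothing says that a patient who leaves off the wristband or misses surveys counts as withdrawn. This stands as a caution. But a rule that can be read either way will not give the same data for every patient, and its plain wording sets an end date for use.

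**The chart is not named as the primary source.** This is correct. The medication list is taken at every monthly contact, and control patients are asked about changes at virtual visits. How fully the record captures outside prescribers is not described. A reader might infer that the endpoint comes from chart review and so need never be missing. The documents support only that it can usually be read there.

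**Section 13 limits the harm itself.** The lost-to-follow-up trigger of 7 months falls after the 6-month visit, so it should seldom cut the primary endpoint unless the last interrogation preceded enrollment. Pregnant subjects stay monitored. The problem is therefore mainly voluntary withdrawal before month 6.

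**Withdrawal that differs by arm is speculation.** The documents give one overall 10%. Unequal withdrawal is possible in an unblinded trial, but the 3+0 split is only an extreme case.

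**The consent form may already make the distinction.** Consent pages were removed from the review copy, so this cannot be checked.

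**Conclusion.** The point holds as a cheap improvement that protects the randomised comparison. Followed as written, section 13 drops or shortens the primary endpoint for patients who withdraw voluntarily before month 6 with no change yet recorded, although the plan already provides for reading medications from the record without visits. Later events are lost to the secondary outcomes in the same way.

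The size is about 3 patients at the planned drop-out. Under the stated assumptions, dropping them overstates the by-arm difference by about 4 to 6 points; truncating them shifts it by about 1 point or less.

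A reader might set the 81.5% power without withdrawals against 68.4% or 75.5% with truncated data and conclude that the fix recovers the gap. It does not. The 81.5% supposes that patients who stop the intervention at month 1 still reach 60% by month 6, whereas the same constant-hazard assumption gives about 21%. With record review continued, power is 70.7% to 74.6%. The benefit is equal observation time and an analysis by randomised arm. It depends on patients allowing record review and on the record being reasonably complete.

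**What to change.** Replace the last sentence of section 13 with two levels of withdrawal:

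- **(a) Stopping study visits, intervention, wristband or app.** The patient stays in the randomised arm for analysis. The record review already planned continues: medications to month 6, and hospitalizations, unplanned visits and vital status to month 12.
- **(b) Withdrawal of permission for record review.** Data are used up to that date only.

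State that record review under (a) is not one of the study activities that end at withdrawal, and that subjects who leave the intervention because of pregnancy are also analysed in their randomised arm. Record the level and its date in the eCRF, and make sure the consent wording supports the choice. In section 17, add one sentence on how level (b) patients with no recorded change before month 6 enter the chi-square test.

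The cost is about one paragraph, one sentence in section 17, one eCRF entry, a consent check, and chart review for about 3 patients. Patients may still decline the review, in which case level (b) applies.
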